#### 6.2.7. Time to Response

TTR is defined, for participants with an objective response per IMWG criteria as determined by investigator, as the time from the date of first dose to the first documentation of objective response that is subsequently confirmed. For participants with EMD at baseline, MR or better cannot be confirmed until a post-baseline EMD assessment is performed and the date of confirmed response cannot be prior to the initial EMD assessment date.

TTR will be calculated in weeks as follows:

$$\text{TTR (weeks)} = (\text{date of first objective response} - \text{date of first dose} + 1) / 7$$

TTR will be summarized using simple descriptive statistics (mean, standard deviation, minimum, median, and maximum).

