### 6.2.3. Duration of Response

DOR is defined, for participants with an objective response per IMWG criteria as determined by investigator, as the time from the first documentation of objective response that is subsequently confirmed, until the date of the first confirmed PD per IMWG criteria, or death due to any cause, whichever occurs first. The rules for PD confirmation are described in [Table 4](#).

DOR will be calculated as follows:

$$\text{DOR (months)} = (\text{date of event or censoring} - \text{first date of objective response} + 1) / 30.4375$$

090177e1a0f4f44c\Approved\Approved On: 14-Jun-2024 22:12 (GMT)

The censoring rules for DOR are as described for PFS in [Section 6.2.2](#), except that participants will not be censored for no adequate post-baseline assessment, as only participants with an objective response are included in the analysis of DOR.

If at least 3 participants across all dose levels achieve an objective response and subsequently have an event, DOR will be estimated using the same Kaplan-Meier method as described for PFS in [Section 6.2.2](#) and displayed graphically where appropriate. Otherwise only listings will be provided.

The DOR rate at 3, 6, 9, and 12 months (and in subsequent 6-month increments while there are participants still at risk) will be estimated with corresponding two-sided 95% CIs.

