#### **6.2.6. Time to Response**

TTR is defined, for participants with an objective response per IMWG criteria as determined by investigator, as the time from the date of first dose to the first documentation of objective response that is subsequently confirmed. For participants with EMD at baseline, MR or better (for those with target plasmacytomas) and CR or better (for those with non-target non-bone EMD only) cannot be confirmed until a post-baseline EMD assessment is performed and the date of confirmed response cannot be prior to the initial EMD assessment date.

TTR will be calculated in weeks as follows:

$$\text{TTR (weeks)} = (\text{date of first objective response} - \text{date of first dose} + 1) / 7$$

TTR will be summarized using simple descriptive statistics (mean, standard deviation, minimum, median, and maximum).

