### 3.2.1.7. Time to Response

Time to response (TTR) is defined, for participants with an objective response per IMWG criteria as determined by investigator, as the time from the date of first dose to the first documentation of objective response observed date that is subsequently confirmed. For participants with EMD at baseline, MR or better cannot be confirmed until a post-baseline EMD assessment is performed and the date of confirmed response cannot be prior to the initial EMD assessment date.

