## 6.2. Secondary Efficacy Endpoints

### 6.2.1. Objective Response

The observed point estimate of ORR will be calculated along with the 2-sided 95% CIs using the Clopper-Pearson method (exact CI for a binomial proportion).

The frequency (number and percentage) of participants with BOR by investigator in each response category will be summarized: sCR; CR; VGPR; PR; MR; SD; PD; Not evaluable (NE).

In addition, the following response categories will be calculated along with corresponding 2-sided exact 95% CIs using the Clopper-Pearson method:

- VGPR or better (sCR + CR + VGPR);
- Clinical benefit (sCR + CR + VGPR + PR + MR).

BOR will be assessed based on reported timepoint responses by investigator recorded at evaluation time points from the date of first dose until confirmed disease progression, death or start of new anticancer therapy using IMWG response criteria. BOR needs to be confirmed according to IMWG response criteria ([Table 2](#)). If a participant meets multiple criteria in determining confirmed BOR, the order of criteria in this table will be used to define the hierarchy. Twenty-eight days is required between the disease assessments, but a different sample is required for confirmation. A confirmatory response assessment may be performed >28 days following the initial response assessment, allowing for a maximum of 1 intervening missing or not evaluable assessment.

The rules for PD confirmation apply to both confirmed PD as BOR and confirmed PD after BOR (for time-to-event endpoint analyses), and the PD date is the date of the initial documentation of PD date.

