**Table 2. Derivation Rules for Confirmed Best Overall Response per IMWG Response Criteria**

Scenario	Timepoint Response at:			BOR
	Assessment 1	Assessment 2	Assessment 3	
1	sCR	sCR		sCR
2	sCR	NE	sCR	
3	CR/VGPR/PR/MR/SD/PD c	sCR	sCR	
4	CR	sCR/CR		CR
5	sCR/CR	CR		
6	CR	NE	CR	
7	VGPR/PR/MR/SD/PD c	CR	CR	
8	VGPR	sCR/CR/VGPR		VGPR
9	sCR/CR/VGPR	VGPR		
10	VGPR	NE	VGPR	
11	PR/MR/SD/PD c	VGPR	VGPR	
12	PR	sCR/CR/VGPR/PR		PR
13	sCR/CR/VGPR/PR	PR		
14	PR	NE	PR	
15	MR/SD/PD c	PR	PR	
16	MR	sCR/CR/VGPR/PR/MR		MR
17	sCR/CR/VGPR/PR/MR	MR		
18	MR	NE	MR	
19	SD/PD c	MR	MR	
20	SD	No further assessments		SD a
21	SD	sCR/CR/VGPR/PR/MR /SD/PD	No further assessments	
22	sCR/CR/VGPR/PR/MR	NE/PD or no further assessment	No further assessments	
23	PD c	PD (any reason) including PD after initiation of new anticancer therapy		PD
24	PD c	Participant died due to disease before further disease assessment (including death due to disease under study after initiation of new anticancer therapy)		

090177e1993a4a6d\Approved\Approved On: 31-Jan-2022 16:54 (GMT)

Scenario	Timepoint Response at:			BOR
	Assessment 1	Assessment 2	Assessment 3	
25	PD (due to EMD, or bone marrow plasma cells) b	sCR/CR/VGPR/PR/MR /SD/NE/PD or no further assessments	No further assessments	
26	Death (due to disease under study)			
27	Death (not due to disease under study) before initiation of new anticancer therapy			
28	NE	No further assessment		
29	NE	NE/PD c	No further assessments	NE
30	PD c	sCR/CR/VGPR/PR/MR /SD/NE	No further assessments	
EMD = extramedullary disease; IMWG = International Myeloma Working Group, sCR = stringent complete response, CR = complete response, PR = partial response, VGPR = very good partial response, SD = stable disease, PD = progressive disease, NE = not evaluable. a. SD does not need to be confirmed. b. PD due to EMD (includes any new lesion, increased extramedullary or paramedullary lesions, plasmacytomas), or bone marrow plasma cells does not need to be confirmed. c. PD due to reasons other than EMD, or bone marrow plasma cells.				

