### 6.2.2. Complete Response Rate

CRR is defined as the proportion of participants with a confirmed CR/sCR per IMWG criteria as determined by investigator.

Point estimates of CRR will be calculated along with corresponding 2-sided exact 95% CIs using the Clopper-Pearson method.

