#### 6.2.4. Duration of Response

DOR is defined, for participants with an objective response per IMWG criteria as determined by investigator, as the time from the first documentation of objective response that is subsequently confirmed, until the initial documentation of PD date that is subsequently confirmed per IMWG criteria, or death due to any cause, whichever occurs first. The rules for PD confirmation are described in [Table 2](#).

DOR will be calculated as follows:

$$\text{DOR (months)} = (\text{date of event or censoring} - \text{first date of objective response} + 1) / 30.4375$$

The censoring rules for DOR are as described for PFS in [Section 6.2.2 in the master SAP](#) except that participants will not be censored for no adequate post-baseline assessment, as only participants with an objective response are included in the analysis of DOR.

If at least 3 participants achieve an objective response and subsequently have an event, DOR will be estimated using the same Kaplan-Meier method as described for PFS in [Section 6.2.3](#) and displayed graphically where appropriate. Otherwise only listings will be provided.

The DOR rate at 3, 6, 9, and 12 months (and in subsequent 6-month increments while there are participants still at risk) will be estimated with corresponding two-sided 95% CIs.

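### The extramedullary-disease rule for confirming and dating a response is missing from Sub-study B's best-response derivation and, in both sub-studies, from duration of response

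*SAP*

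**What the plan says.** **Sub-study B SAP.** The EMD rule is stated twice, both times under time to response. Section 3.2.1.7 says "For participants with EMD at baseline, MR or better cannot be confirmed until a post-baseline EMD assessment is performed", and 6.2.7 repeats it: "MR or better cannot be confirmed until a post-baseline EMD assessment is performed and the date of confirmed response" may not fall before the EMD assessment. Section 3.2.1.7 has the same date limit.

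The other response endpoints do not mention the rule:

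- Section 6.2.1 says "BOR needs to be confirmed according to IMWG response criteria" and refers to Table 2. The response rows of that table use only the sequence of investigator timepoint responses. EMD enters only through progression: "PD due to EMD (includes any new lesion, increased extramedullary or paramedullary lesions, plasmacytomas), or bone marrow plasma cells does not need to be confirmed".
- Section 6.2.2: "CRR is defined as the proportion of participants with a confirmed CR/sCR per IMWG criteria as determined by investigator".
- Section 6.2.4 defines DOR "as the time from the first documentation of objective response that is subsequently confirmed", with no limit on the start date.

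**Sub-study A SAP.** Section 6.1.2 places the confirmation half in the BOR text. It covers MR or better for participants with target plasmacytomas, and only CR or better for those whose EMD is entirely non-target and non-bone. The date half, "the date of confirmed response cannot be prior to the initial EMD assessment date", is found only in 6.2.6 under time to response. Section 6.2.3 defines DOR "as the time from the first documentation of objective response that is subsequently confirmed, until the date of the first confirmed PD", again with no floor.

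The master SAP's response, TTR and DOR sections contain no EMD rule for response that either sub-study could inherit.

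**The concern.** A SAP is programmed section by section, and a condition written under one endpoint will be applied to that endpoint. Two inconsistencies follow for participants with baseline EMD.

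First, in Sub-study B a participant with two consecutive recorded PRs and no repeat EMD assessment is a responder in ORR, while the TTR section says that the same response is not confirmed. CRR has the same gap.

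Second, in both sub-studies the TTR response date is held back to the EMD assessment while the DOR start is not, so one participant can have two dates for one response. This error has one direction: it can only lengthen DOR.

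At stake are secondary endpoints: ORR, CRR and DOR in Sub-study B, and DOR in Sub-study A.

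**Working it through.** The plan gives no figure to reproduce here. The check sets the rules side by side and then applies the SAPs' own formulas to an assumed timeline.

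**1. Where each half of the rule is written**

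| Endpoint | Sub-study A | Sub-study B |
|---|---|---|
| BOR, ORR, CRR: confirmation | present (6.1.2) | absent (6.2.1, Table 2, 6.2.2) |
| TTR: date floor | present (6.2.6) | present (3.2.1.7, 6.2.7) |
| DOR: date floor | absent (6.2.3) | absent (6.2.4) |
| DOCR: date floor | not stated; formula starts at the confirmed sCR/CR date (6.2.4) | not stated; formula starts at the confirmed CR/sCR date (6.2.5) |

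**2. ORR in Sub-study B.** Under Table 2, scenario 12, PR followed by PR gives a BOR of PR. No row asks whether EMD was re-assessed, so the participant enters the ORR numerator. Up to 20 participants are planned at the RP2D (5.1.1.2), so each such case moves ORR by 1/20 = 5 points. For illustration, with exact 95% intervals: 13/20 = 65% (40.8 to 84.6) against 12/20 = 60% (36.1 to 80.9).

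**3. DOR in both sub-studies.** The formulas are TTR (weeks) = (response date − first dose date + 1)/7 and DOR (months) = (event date − response date + 1)/30.4375. Assumed timeline, in study days: first recorded PR on day 36, progression on day 300, first post-baseline EMD assessment on day 64, 92, 120 or 176. The initial EMD assessment is read as the first one after baseline, because a floor at baseline would have no effect.

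- TTR without the floor: 36/7 = 5.1 weeks.
- DOR as written: (300 − 36 + 1)/30.4375 = 8.71 months in every case.

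| EMD assessment | TTR with floor (weeks) | DOR with same floor (months) | Excess in DOR as written (months) |
|---|---|---|---|
| Day 64 | 64/7 = 9.1 | 237/30.4375 = 7.79 | 28/30.4375 = 0.92 |
| Day 92 | 92/7 = 13.1 | 209/30.4375 = 6.87 | 56/30.4375 = 1.84 |
| Day 120 | 120/7 = 17.1 | 181/30.4375 = 5.95 | 84/30.4375 = 2.76 |
| Day 176 | 176/7 = 25.1 | 125/30.4375 = 4.11 | 140/30.4375 = 4.60 |

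The excess is always the time from first recorded response to first EMD assessment. It does not depend on when progression occurs.

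**4. Consistency check.** With a single response date, TTR + DOR − 1 day must equal PFS for a participant who responds and then progresses. Take the day 92 case, where PFS is 300 days. As written, 92 + 265 − 1 = 356 days, so 56 days are counted in both TTR and DOR. With one floored date, 92 + 209 − 1 = 300 days.

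**The case against.** The strongest reply is that the rule is worded generally. It says that a response cannot be confirmed, not that it cannot be confirmed for TTR. It also reaches down to MR, which is not an objective response, so it looks meant for more than TTR. TTR and DOR share the same defining phrase, and TTR is restricted to objective responders, so one confirmation status and one date may be intended. That may well be the intention, but neither SAP says so. Sub-study A makes the point: its authors put the confirmation half under BOR and still left the date floor under TTR alone.

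A second reply is that the protocol already guards ORR. In Appendix 11, where soft tissue plasmacytomas are present at baseline, their reduction is part of MR, PR and VGPR, their disappearance is part of CR, and the lowest level across parameters applies. Section 8.1.3 requires serial monitoring of baseline plasmacytomas. An investigator following this should not record PR on biochemistry alone. This stands as a real limit on how often the ORR problem can arise. It does not close the gap, because footnote a of the same appendix says that imaging is generally not needed to satisfy the response categories. The EMD rule would also be unnecessary if early biochemical responses were never recorded.

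A third reply concerns duration of complete response (DOCR), and it stands. A reader might infer that DOCR is overstated in the same way as DOR. The documents do not support that: the DOCR formulas in both SAPs start from the date of the confirmed complete response, which is the term that the floor governs. DOCR is ambiguous rather than clearly wrong, and it can be affected only if CR is recorded before the EMD assessment.

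**Conclusion.** The point holds for a defined subset: baseline-EMD participants covered by the rule whose response is recorded before, or without, a post-baseline EMD assessment. For them the Sub-study B SAP read literally contradicts itself on whether a response is confirmed, and both SAPs give TTR and DOR different response dates. DOR is too long by the gap, 0.92 to 4.60 months for gaps of 28 to 140 days. Sub-study B ORR moves by 5 points per misclassified participant at n=20. The timelines are assumptions, because the imaging schedule is not in these documents.

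Three stronger readings are not supported:

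- **That Sub-study A's primary ORR is affected.** It is not, because 6.1.2 carries the confirmation rule.
- **That DOR is too long for every EMD responder.** It is not. Where EMD is re-assessed by the time response is first recorded, the two dates agree. In Sub-study A, participants with only non-target non-bone EMD are limited only for CR or better, so a DOR starting at an earlier PR is unaffected.
- **That an assumed EMD share gives the number misclassified.** A share of 15 to 30% of 20 would be 3 to 6 participants with EMD, but that is not the number never re-assessed. The documents do not give that number; it may be small and could be zero.

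No hypothesis test or go/no-go threshold depends on the point. It is still worth correcting, because the stated rules conflict and the DOR bias has a known direction.

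**What to change.** 1. In Sub-study B 6.2.1, with a note to Table 2, state the EMD confirmation rule so that it governs BOR, ORR and CRR. While moving it, say whether it is to cover all baseline EMD, as now worded, or to follow Sub-study A's split between target and non-target disease.
2. In both sub-study SAPs, define one derived response date and use it for TTR and DOR. Define the corresponding complete-response date for DOCR. For participants whom the rule covers, neither date may precede the first post-baseline EMD assessment; write first post-baseline rather than initial.

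The cost is SAP wording and one shared derived variable. No data collection or clinical conduct changes. ORR in Sub-study B and DOR in both sub-studies may become slightly less favourable.

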#### 6.2.8. Minimal Residual Disease Negativity Rate

MRD negativity rate is defined as the proportion of participants with CR or better by investigator and negative MRD (assessed by central lab) per IMWG sequencing criteria at any time from the date of first dose until the first documentation of confirmed PD, death or start of new anticancer therapy, whichever occurs first. The rules for PD confirmation are described in [Table 2](#).

MRD negativity will be defined by two thresholds, CCI.

The MRD negativity rate will be calculated along with the 2-sided 95% CI using the Clopper-Pearson method as follows:

- MRD negative with confirmed sCR/CR based on the Safety Analysis Set;

- MRD negative based on the subset who achieved confirmed sCR/CR in the Safety Analysis Set;
- MRD negative based on the subset of MRD evaluable patients (achieve sCR/CR and have at least one MRD assessment).

### 6.3. Other Secondary Endpoints

#### 6.3.1. Pharmacokinetic/Pharmacodynamics

Pharmacokinetic parameter analyses will be based on the PK Analysis Set.

##### 6.3.1.1. Elranatamab

PK data analyses will include descriptive summary statistics of the predose and postdose serum concentrations, and PK parameters of elranatamab by study visit and time point. Box and Whisker plots for predose elranatamab concentrations by study visit and PK parameters ( $C_{max}$  and  $AUC_{last}$ ) will be generated. Values below the limit of quantitation for elranatamab and other analytes will be treated as zero in the descriptive statistics calculations. For additional details on handling missing and BLQ values, please refer to [Section 5.3.1 in the master SAP](#).

In addition, the PK data from this study may be used to develop a population PK model. PK data from this study maybe pooled with other studies for population PK model development. The correlations between elranatamab exposure parameters and pharmacodynamic biomarker, efficacy and/or safety outcomes will be explored if data allows. The results of these modeling analyses will be reported separately from the clinical study report.

##### 6.3.1.2. Lenalidomide

PK data analyses will include descriptive summary statistics of predose serum concentrations of lenalidomide by study visit and time point. Box and Whisker plots for predose serum concentrations of lenalidomide by study visit will be generated. PK data from this study maybe pooled with other studies for population PK model development. The correlations between lenalidomide exposure parameters and pharmacodynamic biomarker, efficacy and/or safety outcomes will be explored if data allows. The results of these modeling analyses will be reported separately from the clinical study report.

#### 6.3.2. Immunogenicity

Immunogenicity data will be analyzed in the Immunogenicity Analysis Set.

The percentage of participants with positive ADA will be summarized. Listings and summary tabulations of the ADA data at baseline and post-baseline will be generated. Samples may also be analyzed for the presence of neutralizing antibodies (NAb), and any data will be similarly summarized. For participants with positive ADA or NAb, the magnitude (titer), time of onset, and duration of ADA or NAb response will also be described, if data permit.

The potential impact of immunogenicity on PK and clinical response including pharmacodynamic markers, safety/tolerability and efficacy will be explored, if warranted by the data. This analysis may be reported separately from the CSR.

## **6.4. Exploratory Endpoints**

### **6.4.1. Efficacy Analysis**

#### **6.4.1.1. Sustained MRD Negativity Rate**

sMRD negativity rate will be summarized at pre-specified timepoints. Sustained xx-month MRD negativity rate is defined as the proportion of participants with negative MRD and confirmed sCR/CR with at least xx months apart without positive MRD in between, where xx=12 and 24 months and other timepoints of interest. Sustained xx-month MRD negativity rate will be calculated along with the 2-sided 95% CI using the Clopper-Pearson method.

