10.11. Appendix 11: IMWG Response Criteria for Multiple Myeloma

Participants must have measurable disease at enrollment (study entry) as defined by:

- Serum M protein ≥ 0.5 g/dL (5 g/L);
- Urine M protein ≥ 200 mg/24 hours;
- Serum FLC assay: involved FLC level ≥ 10 mg/dL (≥ 100 mg/L) AND abnormal serum immunoglobulin kappa to lambda FLC ratio (< 0.26 or > 1.65).

Whenever more than 1 parameter is used to assess response, the overall assigned level of response is determined by the lowest level of response.

All response assessments will be entered on the CRF.

All response categories require 2 consecutive assessments made any time before starting new therapy. To confirm response or PD, 2 discrete samples are required, and testing cannot be based upon the splitting of a single sample.

Response ^a	Modified IMWG Criteria
Sustained MRD-negative	
 • CR as defined below plus: • MRD negativity in the marrow (NGF or NGS, or both) and by imaging as defined below, confirmed minimum of 1 year apart. Subsequent evaluations can be used to further specify the duration of negativity (eg, MRD-negative at 5 years)
Flow MRD-negative	
 • CR as defined below plus: • Absence of phenotypically aberrant clonal plasma cells by NGF on BMA using the EuroFlow standard operation procedure for MRD detection in MM (or validated equivalent method) with a minimum sensitivity of 1 in 10^5 nucleated cells or higher
Sequencing MRD-negative	
 • CR as defined below plus: • Absence of clonal plasma cells by NGS on BMA in which presence of a clone is defined as less than 2 identical sequencing reads obtained after DNA sequencing of BMA using the LymphoSIGHT platform (or validated equivalent method) with a minimum sensitivity of 1 in 10^5 nucleated cells or higher
Imaging plus MRD-negative	
 • CR as defined below plus: • MRD negativity as defined by NGF or NGS plus disappearance of every area of increased tracer uptake found at baseline or a preceding PET/CT or decrease to less mediastinal blood pool SUV or decrease to less than that of surrounding normal tissue

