#### **6.4.1.2. Duration of MRD Negativity**

If data permits, DOMRD will be analyzed using Kaplan-Meier method in participants who have achieved negative MRD and confirmed sCR/CR. DOMRD is defined, for participants with negative MRD, as the time from first documentation of negative MRD to the date of first documentation of relapse or death due to any cause. Relapse is defined as any one or more of the following criteria:

- Loss of MRD negative state (evidence of clonal plasma cells on NGF or NGS, or positive imaging study for recurrence of myeloma);
- Reappearance of serum or urine M-protein by immunofixation or electrophoresis;
- Development of  $\geq 5\%$  clonal plasma cells in the bone marrow;
- Appearance of any other sign of progression.

The following exploratory endpoints analyses may be performed. The results may be presented separately from the main CSR.

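### Sub-study B's sustained MRD-negativity rate has no stop at progression or new therapy and ignores relapse seen outside the marrow, so it can disagree with the duration of MRD negativity

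*SAP*

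**What the plan says.** Four places bear on this point.

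- **Sub-study B SAP 6.4.1.1 (exploratory).** The sustained rate is "the proportion of participants with negative MRD and confirmed sCR/CR with at least xx months apart without positive MRD in between". The planned values of xx are 12 and 24, and others may be added. The rate is to be "calculated along with the 2-sided 95% CI using the Clopper-Pearson method". No observation window, imaging condition or denominator is given.
- **Sub-study B SAP 6.2.8 (secondary).** The basic MRD rate uses central-laboratory sequencing in participants with CR or better, and counts results only "until the first documentation of confirmed PD, death or start of new anticancer therapy, whichever occurs first". Section 3.2.1.8 sets the same limit. Section 6.4.1.1 neither repeats nor cites it.
- **Sub-study B SAP 6.4.1.2 (exploratory).** Duration of MRD negativity (DOMRD) ends at relapse or death. The first relapse criterion is loss of the MRD-negative state, described as "evidence of clonal plasma cells on NGF or NGS, or positive imaging study for recurrence of myeloma". The second is "Reappearance of serum or urine M-protein by immunofixation or electrophoresis". The others are at least 5% clonal marrow plasma cells and any other sign of progression. New anticancer therapy is not an event.
- **Protocol Appendix 11.** The row for sustained MRD-negative asks for CR plus "MRD negativity in the marrow (NGF or NGS, or both) and by imaging as defined below, confirmed minimum of 1 year apart".

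**The concern.** Sections 6.4.1.1 and 6.4.1.2 are adjacent and both describe how long MRD negativity lasts, but they disqualify on different evidence. The rate looks only at MRD results between the two negative samples. The duration also looks at imaging, M-protein, plasma-cell percentage and other progression. One participant can therefore be reported as sustained negative in one table and relapsed in the next.

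Two further matters are separate from that conflict. With no window, a negative marrow result obtained after a new anticancer therapy could be credited to elranatamab, lenalidomide and dexamethasone. And a reader who knows Appendix 11 will take the term to mean that imaging was negative too, which the SAP definition does not require.

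**Working it through.** The documents give no rate, sample size or power for this endpoint, so there is no planned figure to reproduce. The check compares the two rules and then sizes one reclassification.

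**1. Compare the rules.** Assume two MRD-negative marrow samples at least xx months apart, a confirmed sCR/CR, and no positive MRD result between the samples except in the first row.

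| Event between the two samples | 6.4.1.1 read literally | 6.4.1.2 |
|---|---|---|
| Clonal cells on sequencing | Fails | Relapse |
| Positive imaging only | Still sustained | Relapse |
| M-protein returns, marrow sequencing negative | Still sustained | Relapse |
| At least 5% clonal plasma cells, no MRD result at that time | Still sustained | Relapse |
| Other sign of progression, marrow negative | Still sustained | Relapse |
| New anticancer therapy, no relapse | Still sustained | No event |

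The rules agree in the first row and conflict in the next four. In the last row they do not conflict. That row shows only that 6.4.1.1 lacks the limit in 6.2.8.

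**2. One illustrative case (months assumed).** Marrow is negative at months 6 and 18, and M-protein is detectable by immunofixation at month 10 and gone again by month 18. The gap is 18 − 6 = 12 months with no positive MRD result, so 6.4.1.1 counts 12-month sustained negativity. Section 6.4.1.2 records relapse 10 − 6 = 4 months after the first negative result.

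This need not be progressive disease. For serum M-protein, Appendix 11 asks for a rise of at least 25% with an absolute increase of at least 0.5 g/dL (a different threshold applies when the lowest value was 5 g/dL or more). A participant below that threshold could stay on treatment and have marrow sampled again.

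**3. Can a sample follow new therapy?** Protocol Section 8.1 lists when disease assessments stop after treatment ends without progression, and new therapy is not on that list. Protocol Section 7.1.2 does list it. The two sections leave such samples possible, and 6.4.1.1 would not exclude them.

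**4. Size of one reclassification.** Section 2.2 of the sub-study B SAP gives up to 20 participants at the RP2D. If that is the denominator, one participant is 1/20 = 5 percentage points. With exact 95% Clopper-Pearson intervals and assumed counts:

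| Count read literally | Count with one fewer |
|---|---|
| 1/20 = 5% (0.1% to 24.9%) | 0/20 = 0% (0% to 16.8%) |
| 8/20 = 40% (19.1% to 63.9%) | 7/20 = 35% (15.4% to 59.2%) |
| 10/20 = 50% (27.2% to 72.8%) | 9/20 = 45% (23.1% to 68.5%) |

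Section 6.2.8 also uses smaller denominators (participants in CR, and MRD-evaluable participants). If 6.4.1.1 used one of those, the shift per participant would be 1/n and so larger.

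**The case against.** The strongest reply is that most of the protection is already there.

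- Section 6.4.1.1 requires confirmed sCR/CR as well as negative MRD. CR under Appendix 11 means negative immunofixation, no soft-tissue plasmacytoma and under 5% marrow plasma cells, with no known progression or new lesions if imaging was done. Someone still relapsed at the second sample would not be in CR.
- Section 3.2.1 stops best overall response at confirmed progression, death or new therapy, and Section 6.2.8 stops the basic MRD rate there too. A programmer might carry both limits across.
- Protocol Section 8.1.2 sends marrow for central MRD testing in suspected or actual CR, so few samples should follow progression.

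This narrows the problem but does not close it. Requiring CR at both samples still allows a relapse between them that has reversed, or imaging evidence outside the CR definition. The response window bounds the sCR/CR, not the later MRD sample. The 6.2.8 window can be assumed, but it is not stated.

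Several stronger readings are tempting and not supported:

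- *New therapy makes the two endpoints contradict each other.* It does not, because 6.4.1.2 has no new-therapy event.
- *All four relapse criteria are loss of the MRD-negative state.* Only the first is so described. The other three are separate relapse criteria, although any of them ends DOMRD.
- *The rate is biased upward.* The literal rule can only count as many participants as the tighter rule or more, but the documents do not show that anyone would be affected.
- *The SAP departed from the protocol on imaging.* This SAP follows Amendment 6, and the protocol's amendment history says Amendment 7 later listed the full modified IMWG criteria in Appendix 11. Version lag is a sufficient explanation.

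**Conclusion.** The point holds as a drafting gap in an exploratory endpoint. Read literally, Section 6.4.1.1 can count as sustained MRD-negative a participant whom 6.4.1.2 counts as relapsed, by any of four types of event. It also lacks the progression, death and new-therapy limit of the basic MRD rate. Both gaps are internal to the SAP, so version lag does not explain them. The difference from Appendix 11 on imaging is real against the current protocol but may be lag.

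No decision rule or error rate is affected. The number of participants affected cannot be derived. The 5-point shift per participant assumes a denominator of 20, which 6.4.1.1 does not state.

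**What to change.** In sub-study B SAP Section 6.4.1.1:

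1. Require both negative MRD results to fall within the window of Section 6.2.8.
2. Count any Section 6.4.1.2 relapse criterion met between the two results as failure to sustain.
3. Name the rate 'sustained marrow MRD negativity', and reserve the Appendix 11 term for participants whose available imaging is also negative.
4. State the denominator.

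Items 1, 2 and 4 are changes of wording and programming. Item 3 is labelling. It does not assume that imaging exists at every MRD time point: imaging times are in the sub-study schedule of activities, which is not among the documents, so the stricter category may be available only for some participants. The downside is that the reported rate may be slightly lower.
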